Appendix 2 Schedule of Assessments – NTDT Population

	Screening	Baseline	Double-blind, Placebo-controlled Treatment											EOT ^a / ET	End of Study (Safety FU)
Visit number	1	2	3	4	5	6	7	8	9	10	11	12	13	14	
Study Week(s)	-4 to 0	NA	1	2	4	8	12	16	20	24	28	32	36	40	
Study Day(s)	-28 to -1	1^b	7±2	14±2	28±5	56±7	84±7	112±7	140±7	168±7	196±7	224±7	252±7	280±7	
On-site visits	X	X	X		X	X	X	X	X	X	X	X	X	X	
Telephone visits ^c				X											
Informed consent	X														
PGx ICF and blood draw (optional) ^d	X														
Demographic information	X														
Medical/disease history ^e	X														
Inclusion/exclusion criteria	X	X													
ECOG score	X														
Clinically indicated virology (Hep A, B, and C and HIV)	X														
Historical transfusion burden ^f	X	X													
Randomization		X													
Vital signs ^g	X	X	X		X	X	X	X	X	X	X	X	X	X	
Weight	X	X	X		X	X	X	X	X	X	X	X	X	X	
Height	X														
Transfusion burden ^h					X	X	X	X	X	X	X	X	X	X	

	Screening	Baseline	Double-blind, Placebo-controlled Treatment										EOT ^a / ET	End of Study (Safety FU)
Visit number	1	2	3	4	5	6	7	8	9	10	11	12	13	14
Study Week(s)	-4 to 0	NA	1	2	4	8	12	16	20	24	28	32	36	40
Study Day(s)	-28 to -1	1 ^b	7±2	14±2	28±5	56±7	84±7	112±7	140±7	168±7	196±7	224±7	252±7	280±7
Physical examination ⁱ	X	X	X		X	X	X	X	X	X	X	X	X	X
12-Lead ECG ^j	X	X	X		X	X	X	X	X	X	X	X	X	X
Hematology and chemistry	X	X	X		X	X	X	X	X	X	X	X	X	X
Coagulation studies	X					X			X				X	
Urinalysis	X	X			X		X			X			X	
Pregnancy testing ^k	X	X	X		X	X	X	X	X	X	X	X	X	X
Specialty hematology ^l	X	X			X		X			X			X	
PD markers ^m	X	X			X		X			X			X	
IMR-687 plasma PK ⁿ		X	X		X					X			X	
QOL assessments ^o		X				X			X				X	
Study drug admin at site ^p		X	X		X	X	X	X	X	X	X	X	X	
Study drug dispensing		X			X	X	X	X	X	X	X	X		
Study drug admin		Oral administration of IMR-687 or placebo qd												
AEs and concomitant medications		Continuous ^q												

AEs = adverse events; ECG = electrocardiogram; ECOG = Eastern Cooperative Oncology Group; ET = early termination; EOT = end of treatment; FU = follow-up; Hb = hemoglobin; HIV = human immunodeficiency virus; hsCRP = highly sensitive C-reactive protein; ICAM-1 = intercellular adhesion molecule 1; ICF = informed consent form; NTDT-PRO = non- -thalassemia patient reported outcome; NT-proBNP = N-terminal pro B-type natriuretic peptide; PD = pharmacodynamics; PE = physical

examination; PGx = pharmacogenomics; PK = pharmacokinetic; pRBC = packed red blood cells; QOL = quality of life; RBC = red blood cell; SD = standard deviation; SF-36 = Short Form (36) Health Survey; TEAE = treatment-emergent adverse event; TIBC = total iron binding capacity; VCAM-1 = vascular cell adhesion molecule

1.

Note: Unless otherwise specified, all assessments should be completed prior to dosing at any given timepoint.

Note: In the case of a subject receiving a transfusion after signing the ICF, but prior to randomization, the investigator would inform the medical monitor. The intent is to avoid transfusions within the 2-week period leading to randomization. Approval could be obtained for the screening period to be extended by a maximum of 14 days.

Note: Unscheduled visits may occur, limited to visits resulting from potential TEAEs, drug dispensation, or other urgent study-related procedures.

a The last day of dosing will be at Week 36 visit; subject should consume their last dose of study drug on site, after pre-dose assessments have been completed. The Week 36 visit will also be the ET visit. During the study visit, assessments should be collected from any subject who discontinues study drug or study prematurely. Early termination visits will have the same procedures as the Week 36 visit, except that study drug will not be administered and trough PK will not be collected.

b The first day study drug is taken is considered Baseline (Day 1). Day 1 assessments should be performed prior to study drug administration. If a subject requires a transfusion on this day, the transfusion may occur only after all study assessments are completed.

c Qualified site personnel will contact the subject by telephone at Week 2 to capture potential TEAEs and concomitant medications. Subjects will also be reminded of compliance with drug and the next visit schedule. If any AEs of significant clinical concern are identified during the telephonic visit, the subject will be requested to come into the site to be assessed.

d Pharmacogenomic evaluation is optional and may be performed at screening if subject provides informed consent.

e Disease history should contain a confirmed diagnosis of β -thalassemia or hemoglobin E/ β -thalassemia. Concomitant alpha gene deletion, duplication, or triplication is allowed.

f After obtaining signed informed consent, the subject's transfusion history for the 12 weeks prior to Baseline (Day 1) visit date should be recorded. In order to be eligible for the study, the dates of transfusion events and the number of pRBC units per event within the 12 weeks prior to the Baseline (Day 1) visit must be available. If available, the following data should also be collected for each transfusion event: volume and hematocrit of each pRBC unit, pre-transfusion Hb, and pre-transfusion weight.

g Vital signs include heart rate, respiratory rate, blood pressure, and body temperature. At Day 1 and Week 4, vital signs will be taken pre-dose and 2 hours (\pm 20 minutes) post-dose, during the PK assessments. At all other timepoints, vital signs can be taken irrespective of taking study drug. Vital signs should be consistently measured in either the sitting or semi-supine position.

h Transfusion burden will be assessed using the following variables: dates of transfusion events, number of pRBC units per event, volume and hematocrit of each pRBC unit, pre-transfusion Hb, and pre-transfusion weight.

i Complete PEs will be performed at Screening, Week 24, and Week 36 and will include a general examination including the abdomen, heart, neurological system, skin, extremities, head, eyes, nose, and throat. At all other visits, symptom-directed PEs will be obtained after identification of AEs deemed by the investigator to be of significant clinical concern.

j All ECGs to be performed in triplicate. At Baseline and Week 4, ECGs will be obtained at pre-dose and 2 hours (\pm 30 minutes) post-dose. At all other timepoints, ECGs will be taken pre-dose.

k Females of childbearing potential only. A serum pregnancy test will be performed at screening via central laboratory; all subsequent tests will be urine performed locally (with test kits provided by the central laboratory).

l Includes HbF and percent F cells. Blood samples should be obtained prior to administration of study drug.

m Includes serum ferritin, soluble transferrin receptor, hepcidin-25, haptoglobin, E-selectin, P-selectin, ICAM-1, VCAM-1, hsCRP, serum NT-proBNP, serum iron and TIBC for calculated transferrin saturation, and erythropoietin. Blood samples should be obtained prior to administration of study drug. PD markers will need to be collected prior to RBC transfusion (if applicable).

n At Baseline and Week 4, serial blood samples for IMR-687 and concentrations of metabolite(s) will be drawn pre-dose (within 30 minutes) and at 15 minutes (\pm 5 minutes), 30 minutes (\pm 5 minutes), and 3 hours (\pm 20 minutes) after administration of study drug. A trough blood sample will be drawn pre-dose at Week 1, Week 24, and Week 36. The date/time of the previous dose will be recorded. If a subject requires a transfusion on the day of a PK draw, the transfusion can only be performed after the final PK sampling. For ET visits, a trough blood sample will not be collected. Patients dosed prior to protocol version 5.0 (15 Mar 2021) used the following PK

sampling schedule: At Baseline and Week 4, serial blood samples for IMR-687 and concentrations of metabolite(s) were drawn predose (within 30 minutes) and at 30 minutes (\pm 5 minutes), 1.5 hours (\pm 15 minutes), 4 hours (\pm 15 minutes), 6 hours (\pm 1 hour), and 24 hours (\pm 2 hours) after administration of study drug. On these full profile PK days, food details was also recorded at the clinical sites. A trough blood sample was drawn predose at Week 1, Week 24, and Week 36. Transfusion should not have coincided with Baseline (Day 1) or the Week 4 visit, due to the PK assessment that day. For ET visits, a trough blood sample was not collected.

o Quality of life assessments will be performed by the NTDI-PRO and SF-36 QoL tools. The QoL assessments will be administered at Baseline and at Weeks 12, 24, and 36. Baseline QoL assessments should be completed before administration of study drug.

p On days when study drug is taken in the clinic, food details will also be recorded.

q Adverse events and concomitant medications, including iron chelation therapy and hydroxyurea use, will be recorded at each visit throughout the study from Screening (after signing the ICF) through the end of study visit (Week 40).

Appendix 3 Data Handling Rules

Category	Description	Data Handling Rule
1. Age (years)	Age (years)	Age is collected from Demographics CRF page.
2. First Dose Date/Time of Study Drug	date/time of first dose of study drug	The date and time (24 hr. clock) of the first dose of study drug will be taken from the Study Drug Administration CRF.
3. Last Dose Date of Study Drug	date of last dose of study drug	
The date of the last dose of study drug will be the Date of last dose from the End of Treatment CRF.
 
If it is missing for the IA, DMC, and final analyses use the data cutoff date.
 
If it is missing at the database lock, the date of the last dose of study drug will be imputed as the later of last visit date, last dispensing date (from Drug Accountability CRF), date of Completion/Discontinuation, and death date.

4. Last Visit Date	Date of Last Visit	Date of last visit according to the Clinic Visit CRF.
5. Last Study Participation Date (STDM variable, typically named RFPENDTC)	Last Study Participation Date (STDM variable, RFPENDTC), where SDTM denotes Study Data Tabulation Model	Last study participation date is defined as last known date of contact which would be the later of the following dates: last visit date, date of the last dose, date of Completion/Discontinuation, date of clinical study follow-up, or death date.
6. Study Day Definitions	Study Day for an assessment/event which occurred on or after the start of study drug	Study Day = Date of assessment/event – date of the first dose of study drug + 1.
	Study Day for an assessment/event which occurred on a day prior to the first dose of study drug in the study	Study Day = date of assessment/event – first dose date of study drug in the study.
	Study Day of Randomization	Study Day of Randomization = date of randomization – date of the first dose of study drug in the study + 1. Study Day is 1 if Baseline is on the day of randomization.
	First Dose Day	First Dose Day in the study is defined as the study day of the first dose of study drug in the study (Study Day 1).
	Last Dose Day	Last Dose Day in the study is defined as the study day of the last dose of study drug in the study.
7. Duration of an event	The duration of an event	The duration of an event is defined as (stop date – start date + 1).
8. Multiple assessments for the same visit	Vital Sign, ECG and Laboratory assessments	
 All ECG assessments are to be performed in triplicate. Valid assessments will be averaged to get the analysis value for that visit. Other than for ECG assessments, the last non-missing measurement taken prior to the date/time of first study drug (including unscheduled assessments) will be the analysis Baseline. Windowing will be applied for by-visit analyses. Unscheduled or Screening visits that occurred before the Baseline visit will not be assigned an analysis visit. The early discontinuation visit will be eligible for allocation to an analysis visit.

Category	Description	Data Handling Rule
		
 • If one or more results for a variable are assigned to the same analysis visit, the result with the date closest to the protocol scheduled day will be used in the analysis. If 2 measurements in the same analysis visit window are equidistant from the protocol scheduled study day, the earliest measurement will be used in the analysis. • If multiple assessments are available on the same day (or for the same time point for ECG assessments), then the average of the assessments will be used in the analysis. • If both central and local assessments of the same lab test are available on the same day, the central result will take precedence over the local result. • All data will be listed in data listings.
9. Special Lab Value Handling	Lab values with a prefix such as: '>', '<', '+' and 'Less than' Etc.	
 • '>': use the available original value +0.001 in the analyses. • '<': use the available original value -0.001 in the analyses. • '+': use the available original value without the prefix in the analyses. • '≥': use the available original value in the analyses. • '≤': use the available original value in the analyses.
10. Prior and concomitant, medication / treatment	Prior, concomitant, and post-treatment medication/treatment	
 • Any medication that was used at any time prior to the date of first study drug is a Prior Medication. • Any medication that was used at any time on or after the date of first study drug and within 30 days of the last dose of study drug is a Concomitant Medication. • If the date of first study medication is missing, then the date of randomization is used (as long as the subject is known to have received study drug on at least one day during the study). Otherwise, in the case of missing dates, any period (Prior and Concomitant) that is possible based on the available information should be applied.
11. Adverse event	Missing CTCAE severity (toxicity grade)	For the AE summary by CTCAE severity grade, an AE with missing CTCAE severity grade will not be imputed. Imputed values will not be listed in data listings.
	Missing relationship to study drug	For the AE summary by relationship, an AE with a missing relationship to study drug will not be imputed. Imputed values will not be listed in data listings.
	Treatment-emergent adverse event	
An adverse event is considered treatment-emergent if emerges on or after initiation of study drug, or an AE that existed pre-treatment and worsened in severity on or after initiation of study drug, through 30 days after the last dose of study drug.
 
An adverse event that begins on the same date as the first dose of study drug is treatment-emergent if the AE begins after the time of first dose or if the time of AE onset is unknown.

Category	Description	Data Handling Rule
		
If the AE start date is partial/missing, then
 
 • If AE start date is completely missing, then the AE is considered as treatment-emergent. • If both AE start month and day are missing and AE start year is the same or after the first dose year, then the AE is considered as treatment-emergent. • If AE start day is missing and AE start year and month are the same or after the first dose year and month, then the AE is considered as treatment-emergent. 
Missing/incomplete (partial) AE start and end dates will not be imputed for data listings.

12. Treatment Duration (days)	Treatment Duration (days)	Treatment duration is defined as Date of last dose of a study drug - Date of first dose of a study drug +1.
13. Duration of Exposure (days)	Duration of Exposure (days)	Exposure is defined as (Date of the last dose of the study drug – Date of first dose of the study drug + 1).
14. General	Conversion of Duration in Days to Duration in Years/Months/Days	
Duration in Years = Duration in Days/365.25
 
Duration in Months = Duration in Days/30.4375
 
Duration in Weeks = Duration in Days/7

15. Hard coding	Hard coding for data analysis	Hard Coding is not allowed during data analysis unless if agreed in writing by Imara.

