10.1.10 Windowing Conventions

All scheduled study visits are defined relative to Study Day 1, the date of first dose. Scheduled visit windows are defined in Appendix 3. A windowing convention will be used to determine the analysis visit value for a given measurement and will be applicable for all by-visit summaries and analyses for efficacy and safety data. Refer to Table 1 (TDT) and Table 2 (NTDT) for specific visit windows.

Table 1: Visit Windows for Efficacy and Safety Analyses – TDT Population

Safety Analyses – Vital Signs and Weight	
Scheduled Study Visit (Protocol Scheduled Day)	Analysis Visit Window (Study Day)
Baseline	≤ 1
Week 1 (Day 7 ± 2)	2 to 15
Week 3 (Day 21 ± 7)	16 to 32
Week 6 (Day 42 ± 7)	33 to 53
Week 9 (Day 63 ± 7)	54 to 74
Week 12 (Day 84 ± 7)	75 to 95
Week 15 (Day 105 ± 7)	96 to 116
Week 18 (Day 126 ± 7)	117 to 137
Week 21 (Day 147 ± 7)	138 to 158
Week 24 (Day 168 ± 7)	159 to 179
Week 27 (Day 189 ± 7)	180 to 200
Week 30 (Day 210 ± 7)	201 to 221
Week 33 (Day 231 ± 7)	222 to 242
Week 36 (Day 252 ± 7)	243 to 267
Week 40 (Day 280 ± 7)	≥ 268
Safety Analyses – 12-Lead ECG, Hematology (Except Specialty Hematology) and Chemistry	
Scheduled Study Visit (Protocol Scheduled Day)	Analysis Visit Window (Study Day)
Baseline	≤ 1
Week 1 (Day 7 ± 2)	2 to 15
Week 3 (Day 21 ± 7)	16 to 32
Week 6 (Day 42 ± 7)	33 to 64
Week 12 (Day 84 ± 7)	65 to 106
Week 18 (Day 126 ± 7)	107 to 148
Week 24 (Day 168 ± 7)	149 to 190
Week 30 (Day 210 ± 7)	191 to 232
Week 36 (Day 252 ± 7)	233 to 267
Week 40 (Day 280 ± 7)	≥ 268
Safety Analyses – Urinalysis	
Scheduled Study Visit (Protocol Scheduled Day)	Analysis Visit Window (Study Day)
Baseline	≤ 1

Week 3 (Day 21 ± 7)	2 to 53
Week 12 (Day 84 ± 7)	54 to 127
Week 24 (Day 168 ± 7)	128 to 211
Week 36 (Day 252 ± 7)	≥212
Safety Analyses – Coagulation	
Scheduled Study Visit (Protocol Scheduled Day)	Analysis Visit Window (Study Day)
Baseline	≤ 1
Week 12 (Day 84 ± 7)	2 to 127
Week 24 (Day 168 ± 7)	128 to 211
Week 36 (Day 252 ± 7)	≥212
Efficacy Analyses – Specialty Hematology	
Scheduled Study Visit (Protocol Scheduled Day)	Analysis Visit Window (Study Day)
Baseline	≤ 1
Week 3 (Day 21 ± 7)	2 to 53
Week 12 (Day 84 ± 7)	54 to 106
Week 18 (Day 126 ± 7)	107 to 148
Week 24 (Day 168 ± 7)	149 to 190
Week 30 (Day 210 ± 7)	191 to 232
Week 36 (Day 252 ± 7)	≥233
Efficacy Analyses- PD Biomarkers	
Scheduled Study Visit (Protocol Scheduled Day)	Analysis Visit Window (Study Day)
Baseline	≤ 1
Week 3 (Day 21 ± 7)	2 to 53

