A plot will be presented to show the pattern of the SBP and DBP values over time by treatment arm and the combined IMR-687 treatment arms. Mean and SE will be presented in the plot. Additionally, spaghetti plots for SBP and DBP values over time will be provided for 1) individual subjects with maximum post-baseline SBP increased ≥ 20 mmHg and SBP ≥ 150 mmHg and 2) maximum post-baseline DBP increased ≥ 20 mmHg and DBP ≥ 100 mmHg. A shift plot displaying shifts from Baseline heart rate ≤ 100 to maximum heart rate >100 post-Baseline will be provided for each population.

All vital signs will be listed in a data listing. All vital sign tables and listings will be reported on the Safety Analysis Set.

13.6.2.4 12-lead ECGs

The average of triplicate 12-lead ECGs will be performed to evaluate the change from Baseline in ECG parameters (heart rate, PR interval, RR interval, QRS duration, QT interval, and QTcF interval). Descriptive statistics (N, mean, SD, median, Q1, Q3, minimum, and maximum) of ECG parameters will be presented for Baseline, each post-Baseline visit, and change from Baseline to each post-Baseline visit by treatment arm, and the combined IMR-687 treatment arms, for both populations. Study Baseline defined in Section 10.1.2 will be used. At Baseline and Week 3 (TDT Population)/Week 4 (NTDT Population), descriptive statistics will also be presented for change from pre-dose to post-dose. All measurements, including those during unscheduled visits, will be provided in data listings, but only the scheduled measurements will be included in the summary.

The average of the ECG results by visit and parameter will be calculated if two or more of the triplicate ECG values are reported at the visit for baseline or post-baseline visits.

The number of subjects whose baseline or post-baseline QTcF values have exceeded the selected Criteria below, will be summarized with the number and percentage of subjects meeting each criterion, by treatment arm, and the combined IMR-687 treatment arms, and visit (baseline, post-baseline), separately for each population. Subjects with baseline or post-baseline (including unscheduled visits) results meeting any criteria will be counted.

Table 7 PCS Criteria for ECGs

ECGs	Criteria
Parameter	Criteria
QTcF Interval	
 • > 450 msec (males only) • > 470 msec (females only) • > 500 msec
QTcF Interval Increase from Baseline	
 • ≥ 30 msec • ≥ 60 msec

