13.6.5 Pharmacokinetic Analyses

Data from subjects who experience emesis within the PK sampling duration of IMR-687 at Study Day 1 or Week 3 (TDT) or Week 4 (NTDT) visits, will be evaluated on a case-by-case basis for exclusion from concentration-time data and PK analysis descriptive summaries. The individual subject data will be listed.

If a quantifiable pre-dose concentration of IMR-687 is detected at Baseline (Study Day 1) and this concentration is greater than 5% of the corresponding C_{max} , all subject data will be excluded from all concentration-time and PK analysis descriptive summaries but will be included in the subject data listings.

All plasma concentration-time data will be reported to the same number of significant figures as displayed in the bioanalytical data. λ_{az} will be reported up to 4 decimal places and time-related PK parameters ($T_{1/2}$, T_{max} , and T_{last}) will be reported up to 3 decimal places. All other PK parameters will be reported to the same number of significant figures as displayed in the bioanalytical data.

The concentration-time data from subjects with sparse PK sampling collected using the sampling schedule reflected in protocol version 5.0 (15 Mar2021) will be summarized descriptively and included in subject listings and analyzed for population PK. Noncompartmental analysis will not be performed with the PK data collected from these subjects. The concentration-time data from subjects with PK samples collected using the sampling schedule reflected in the prior protocol versions (up to version 4.0; 15 Jan 2020) will be summarized descriptively and listed. The PK data from these subjects will be used for the estimation of PK parameters using noncompartmental analysis. All available PK data from this study will also be used to explore any relationship between IMR-687 exposure and clinical response, PD endpoints, or AEs, as data permit. These data will be analyzed together with PK data from other clinical studies for a population PK analysis, as appropriate. Population PK analysis and other exploratory PK/PD analyses are not within the scope of this SAP and will be detailed in a separate population PK analysis plan.

No analysis visit windows will be applied for reporting of plasma concentration-time data and PK analysis, nominal visit times will be used (i.e., Study Day 1, Week 3 or Week 4).

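### SAP Table 1 assigns a protocol-compliant TDT Week 3 visit on Day 14 or 15 to Week 1, so its vital signs, weight, ECG, hematology and chemistry are missing from the Week 3 by-visit summaries

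*SAP*

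**What the plan says.** Protocol Table 2 and SAP Appendix 1 both set the TDT Week 3 visit at Day 21 with a window of 7 days either side. The Week 1 visit is Day 7 ±2.

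SAP 10.1.10 then defines analysis windows: "A windowing convention will be used to determine the analysis visit value for a given measurement and will be applicable for all by-visit summaries", for safety as well as efficacy. In Table 1 the vital signs/weight block and the ECG/hematology/chemistry block carry the same two rows, "Week 1 (Day 7 ± 2) 2 to 15" and "Week 3 (Day 21 ± 7) 16 to 32". Urinalysis, specialty hematology and PD markers have no Week 1 row, and their Week 3 row reads "Week 3 (Day 21 ± 7) 2 to 53".

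For several results in one window, SAP 10.1.10 and Appendix 3 item 8 both say that "the result with the date closest to the protocol scheduled day will be used in the analysis". If two results are equally distant, the earlier one is used.

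In TDT subjects, ECGs and vital signs are taken before and 2 hours after dosing at Day 1 and at Week 3 (Protocol Table 2, footnotes g and j). ECGs at all other visits are pre-dose only. For Baseline and Week 3, SAP 13.6.2.4 adds that "descriptive statistics will also be presented for change from pre-dose to post-dose". PK is handled differently: "No analysis visit windows will be applied for reporting of plasma concentration-time data and PK analysis, nominal visit times will be used" (SAP 13.6.5).

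**The concern.** An analysis window should contain the whole of the visit window that sites are told to work to. Here it does not. A site that sees a TDT subject on Day 14 or 15 has followed the protocol, yet the SAP does not treat that visit's vital signs, weight, ECG, hematology and chemistry as Week 3 data.

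Week 3 matters more than a routine visit because it is the only TDT visit after Day 1 with 2-hour post-dose ECGs and vital signs, and so the only such look under repeat dosing. Subjects seen early drop out of the Week 3 descriptive rows and of the Week 3 pre-dose to post-dose ECG change. PK from the same visit keeps its Week 3 label. That is a deliberate choice for PK and not a fault in itself, but it means that ECG and PK from one visit can carry different visit labels.

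**Working it through.** **Inputs.** Visit windows: Protocol Table 2 and SAP Appendix 1 (TDT), Protocol Table 3 and SAP Appendix 2 (NTDT). Analysis windows: SAP Tables 1 and 2. Day numbering on and after the first dose: "Study Day = Date of assessment/event – date of the first dose of study drug + 1" (SAP Appendix 3). Tie and closest-day rules: SAP 10.1.10 and Appendix 3 item 8.

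**1. Reproducing the cut.** The window bounds follow one rule: take target days at 7 × week + 1, find the midpoint of adjacent targets, and round down.
- Weeks 1 and 3: (8 + 22)/2 = 15, the printed end of Week 1.
- Weeks 3 and 6: (22 + 43)/2 = 32.5, rounded down to 32, the printed end of Week 3.

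The same rule gives every other bound in the TDT vital-sign, ECG/hematology/chemistry and urinalysis blocks and in the NTDT block for vital signs, ECG and laboratory tests. Table 1 itself prints scheduled days at 7 × week (Days 7 and 21), whose midpoint is (7 + 21)/2 = 14. The cut and the printed scheduled days are therefore one day apart.

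**2. Is each visit window inside its analysis window?**

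| Visit | Allowed days | Analysis window | Days outside |
|---|---|---|---|
| TDT Week 1 | 5–9 | 2–15 | none |
| TDT Week 3 | 14–28 | 16–32 | 14, 15 |
| TDT Week 6 | 35–49 | 33–53 (vital signs), 33–64 (ECG, laboratory) | none |
| NTDT Week 4 | 23–33 | 19–43 | none |

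All remaining visits in those blocks also lie inside their windows. TDT Week 3 is the only exception, with 2 of its 15 allowed days outside.

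**3. What happens to a Day 14 or 15 result.** It enters the Week 1 window, whose scheduled day is 7.
- Its distance from Day 7 is 14 − 7 = 7 or 15 − 7 = 8 days.
- An on-schedule Week 1 result (Days 5–9) is at most 2 days from Day 7, so it always wins and the Week 3 result is not used.
- If there is no Week 1 result for that variable, the Day 14 or 15 result is kept but labeled Week 1.
- No other scheduled visit fills the Week 3 window: the earliest Week 6 visit is 42 − 7 = Day 35, after Day 32.

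The post-dose ECG is a special case. Week 1 has no scheduled post-dose ECG to compete with it, and the SAP does not say whether it is dropped or shown under Week 1. In both cases it is absent from Week 3.

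**4. How many subjects.** The documents give no distribution of visit days, so these are assumptions: all 60 planned TDT subjects attend Week 3 within the allowed window, with either an even spread or normal weights centred on Day 21 and restricted to Days 14–28.

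| Assumed scatter | Share on Day 14 or 15 | Of 60 subjects |
|---|---|---|
| Even over 15 days | 2/15 = 13.3% | 8.0 |
| SD 5 days | 7.9% | 4.8 |
| SD 3.5 days | 4.3% | 2.6 |
| SD 3 days | 2.7% | 1.6 |
| SD 2 days | 0.3% | 0.2 |

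**The case against.** The strongest reply is that little of consequence is touched, and much of that reply stands.

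- **The tables meant to detect safety signals are intact.** QTcF thresholds, vital-sign criteria, and laboratory shift and threshold tables count any post-baseline result, and the listings keep everything. Only by-visit descriptive summaries change.
- **Not all Week 3 data are affected.** Urinalysis, specialty hematology and PD markers keep their Week 3 label because their window is Days 2–53. Coagulation has no Week 3 analysis visit.
- **Week 3 does not hold the only post-dose ECG on treatment.** A reader might infer that it does. Day 1 also has one, 2 hours after the first dose, and the SAP summarizes both. Week 3 is the only one after Day 1.
- **The result is not always discarded.** A reader might infer that from the closest-day rule. The rule works variable by variable, and where no Week 1 result competes the data are mislabeled rather than dropped.
- **The within-visit ECG change is not itself a listed primary endpoint.** SAP section 9.0 lists changes from Baseline and clinically significant criteria; the pre-dose to post-dose change is an additional descriptive summary. Week 3 changes from Baseline in ECG, vital signs and laboratory tests are listed, and they are affected too.

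None of this removes the mismatch. Windowing applies to all by-visit safety summaries, Table 1 has an explicit ECG block, and nominal visits are reserved for PK. No other text returns a Day 14 or 15 visit to Week 3.

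**Conclusion.** The mismatch is real and follows from the documents by day arithmetic alone. It lies in two rows of SAP Table 1, repeated in two TDT blocks; the closest-day rule is sound and only exposes it. It looks like an oversight, because every other visit window checked sits inside its analysis window.

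The effect is small. It is limited to Week 3 by-visit descriptive summaries of vital signs, weight, ECG, hematology and chemistry in TDT subjects, including the Week 3 pre-dose to post-dose ECG change. The number affected cannot be determined from the documents; under the assumed scatters it runs from about 0 to 8 of 60, and the upper end needs visits spread evenly over all 15 allowed days. The documents do not support reading this as a general loss of Week 3 safety data. It is worth correcting because the correction is cheap and the visit is the only one of its kind after Day 1.

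**What to change.** In SAP Table 1, in both the vital signs/weight block and the ECG/hematology/chemistry block for TDT, set Week 1 to Days 2–13 and Week 3 to Days 14–32. Every compliant Week 1 visit (Days 5–9) and every compliant Week 3 visit (Days 14–28) then falls in its own window. Moving the cut only to the midpoint of the printed days would not be enough: Day 14 is 7 days from both Day 7 and Day 21.

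There is one small side effect. An unscheduled result on Day 15 is 6 days from Day 21 and would beat a compliant Week 3 visit on Day 28, which is 7 days away. An unscheduled result on Day 14 would tie with it and win as the earlier. The Week 2 telephone contact (Day 14 ±2) can lead to such a site visit. A sentence in SAP 10.1.10 and Appendix 3 item 8 giving a scheduled visit's result precedence over unscheduled results in the same window prevents this. A Week 1 visit made out of window, on Day 14 or later, would also enter the Week 3 window, but that is already a deviation from the schedule.

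The cost is two changed bounds in each of two blocks plus one sentence, made before database lock. Study conduct and data collection are unaffected.
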